8.2.2. Patient population

The study plans to include a total of 40 patients with metastatic renal cell carcinoma in CR with Sunitinib (**Cases**) and 80 patients with metastatic renal cell carcinoma with no CR receiving Sunitinib throughout the 36 months of the study (**Controls**).

The calculation of this study population size is justified on page 5.0 "Statistical Methods".

. Inclusion and exclusion criteria for Cases:

8.2.3. Inclusion criteria

- Adult patients (≥ 18 years)
- Patients with mRCC confirmed by histological analysis
- Treated with Sunitinib according to a regimen in the text of the SmPC
- Presenting a complete remission in the preceding 5 years (according to RECIST v1.1) with Sunitinib only or combined with localized treatment (surgery, radiotherapy, cryoablation or radiofrequency ablation)
- Patients of childbearing age using a mandatory method of contraception
- Affiliated to a social security scheme
- Informed about the study methods and having given their consent

Exclusion criteria

- Complete remission occurring in the absence of treatment with Sunitinib

8.2.5. Detailed logistics

8.2.5.1. Initiation of the study

The oncologists who agreed to participate in the study during the feasibility study will receive a letter containing:

- A covering letter with a reply slip to be returned to Pfizer's logistics center
- A study synopsis
- The participating physicians' contracts, one copy of which should be returned to Pfizer's logistics center
- A pre-paid envelope

Physicians who did not respond to the emails will be contacted again by telephone fifteen (15) days later until the desired number of participating physicians has been reached.

Once the contract has been signed and returned to Pfizer's logistics center, it will be validated by Pfizer. The physician will be contacted by mail to know if he want a website monitoring visit for his center.

If the physician want a website monitoring visit so this one will be program with his disponibilities. The member of personal Pfizer of each department will be present :

- Post AMM study gestion
- Medical oncology
- Pharmacovigilance

The physician will receive the study website address and his access code. The physician will found on the website the following documents

- CCTIRS opinion
- EC opinion
- CNOM opinion
- CNIL opinion
- Authorization from the Ministry of Research
- The study protocol and protocol amendment
- The memorandum to physicians
- The serious adverse events (SAE) declaration form (Appendix 1)

In addition, data relating to the physician (year of registration, year of doctoral thesis, town where practicing etc.) can be uploaded to the website as well as the anonymized data regarding the patients.

Also, the physician receive by mail :

- A file containing all documents in the paper version of study (protocol, regulatory agreements, etc ...)
- briefings / patient consent
- CD / ROMs and pre postage for mailing envelopes at IGR
- aliquots pellets and pre-labeled and forms for the transport of blood samples
- envelopes sufficient to return the document
- Each physician investigator will be a single number (0001 to 00XX).

The physicians will be presented with a hotline number as well as an email address where they can ask questions about the conducting of the study.

8.2.5.2. Screening of patients

Before any gathering of personal data, the physician will invite the patient to participate in this research and will inform him/her about:

- The objective, the nature of the constraints
- The computer processing of his/her data that will be collected during this research and will also specify his/her rights of access, opposition and rectification of his/her data
- The storage of blood samples for scientific purposes at the end of the research

In addition, during this visit (screening visit), the physician will check the eligibility criteria.

Finally, an information leaflet summarizing these different points will be handed to the patient.

If the patient with metastatic renal cell carcinoma in CR with Sunitinib (Cases) consents to participate in the research, the physician should during the screening visit:

- Obtain his/her express written consent (Appendix 2)
- Complete the screening form and send it, along with the 2 CT scan burnet on 2 CD-ROM, to the IGR.
- Complete the inclusion questionnaire
- Draw 10 ml of blood into 2 EDTA tubes of 5 ml each and send the sample after centrifugation to the IGR
- Collection of a block or in the absence of 15 white slides from a histological sample

If the patient in CR presents disease progression during the 3 years of follow-up:

- Complete the disease progression questionnaire
- Draw 10 ml of blood into 2 EDTA tubes of 5 ml each and send the sample after centrifugation to the IGR
- Collection of a block or in the absence of 15 white slides from a histological sample

If the patient with metastatic renal cell carcinoma without CR with Sunitinib (**Controls**) consents to participate in the research, the physician should:

- Obtain his/her express written consent (Appendix 3)
- Complete the inclusion questionnaire
- Draw 10 ml of blood into 2 EDTA tubes of 5 ml each before starting Sunitinib, at 6 months, at 12 months and during disease progression and send the sample after centrifugation to the IGR.

Receipt and collection of case report forms

The Pfizer project managers will ensure monitoring of incomplete or inconsistent data (checking of inconsistencies, non-responses and omissions) and will be in permanent contact with the physicians.

During the patient screening phase, and based on the number of physicians (no patient enrolled), the project managers will be required to contact these physicians again and remind them about the study deadlines.

8.2.5.3. End of study

The project manager will inform the physician about the end of patient enrollment and will remind him/her again regarding possible missing documents required for remuneration or inconsistencies in the gathered data identified during data management.

8.2.5.4. Roles of those conducting the study

Via its project managers, the logistics center will ensure the telemonitoring as well as the centralized e-monitoring of the participating physicians (use of Pfizer's study management database and the dedicated study website).

The company responsible for the biometrics will ensure the configuration of the eCRF, the issuing of correction requests, the writing of the statistical analysis plan, the statistical report and the clinical report of the study.

The oncologists must ensure the screening of patients and the gathering of case report form data while observing the research protocol as well as the contract.

8.2.5.5. Logistical monitoring

The monitoring of the participating physicians will be done by a team of project managers specially trained for the study. This monitoring may be done in various manners: telephone call, email, specific letter and newsletter.

These contacts will be advantageous because they will promote the involvement of and the quality of the work done by the participating physicians. As far as possible, everyone will be monitored by the same project manager, from their recruitment to close-out of the study.

The project managers will ensure monitoring of incomplete or inconsistent data (checking of inconsistencies, non-responses and omissions) and will be in permanent contact with the participating physicians. During the patient screening phase and depending on the number of inactive participating physicians (no patient screened), the project managers may need to send them reminders.

In addition, a study-specific toll-free number will be provided for use by the participating physicians in order to be able to respond to their questions throughout the study.

In terms of traceability, all of the "incoming" and "outgoing" (screening call, reminder call etc.) calls to this toll-free number will be the subject of a written report (date, reason for call, action required etc.) and will be recorded in dashboards.

8.3. Variables

8.4. Data sources

Inclusion data

Descriptive statistics will be used to describe the patient population and the therapeutic treatment methods. More specifically, this will consist of the demographic profile of the patients, the associated diseases and concomitant treatments, data relating to the initial treatment of the cancer, data relating to disease progression, the kind of localized treatment received that led to the complete remission, data relating to the patient's health status and to the status of the disease at the start of Sunitinib, data relating to the complete remission and the treatment strategy after the complete remission.

End-of-study visit data

The number of deaths and the status of patients will be analyzed.

Supplementary data

Blood samples will be drawn from patients with metastatic renal cell carcinoma in CR with Sunitinib (**Cases**) during complete remission and in the case of disease progression.

Blood samples will be drawn from patients with metastatic renal cell carcinoma in the absence of CR with Sunitinib (**Controls**) before start of Sunitinib, at 6 months, at 12 months and during disease progression.

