If additional treatment with Sunitinib was given after the complete remission (pseudo-adjuvant), could you please indicate the duration |____| (months)

LOCALIZED OR DISTANT PROGRESSION

LOCAL PROGRESSION YES NO

DISTANT PROGRESSION YES NO

If yes: **Progression at a known metastatic site**

Yes No

New metastatic site

Yes No

METASTATIC SITES

LOCALIZATION OF METASTASES	YES	NO
- Lungs		
- Bone		
- Liver		
- Adrenal glands		
- Pancreas		
- Brain		
- Lymph nodes		
o Supradiaphragmatic		
o Infradiaphragmatic		
- Recurrence at the nephrectomy renal bed		
- Other		
(please specify):.....		

BLOOD SAMPLING DURING PROGRESSION

YES NO

- Blood sample of 2 times 5 ml

Sampling date |_____|_____|_____|_____|2|0|1|____| (dd/mm/yyyy)

studyS OF SYSTEMIC TREATMENT OF THE PROGRESSION			
	Route of administration	Duration of administration	Daily dosage
Anti-VEGF			
- Bevacizumab (with interferon)
- Bevacizumab (without interferon)
Tyrosine kinase inhibitor			
- Restart of Sunitinib
- Sorafenib.....
mTOR inhibitor			
- Temsirolimus
- Everolimus.....
Other systemic treatment (please specify)			
.....
.....
.....
SURGICAL TREATMENT			
Please specify:			
.....			
.....			

DATA RELATING TO THE END OF STUDY VISIT (36 months)

*To be completed only if visit took place,
if not, complete the latest information or death form*

Did the patient attend a visit at 36 months YES NO

Visit date | ____ | ____ | ____ | ____ | | 2 | 0 | 1 | ____ | (dd/mm/yyyy)

Best objective response observed since progression

- Complete
- Partial
- Progression
- Stable

Duration of administration of the progression treatment | ____ | ____ | (months)

LATEST INFORMATION OR DEATH FROM

LATEST INFORMATION

Did the patient withdrawn from study prematurely? YES
NO

Latest information date: | ____ | ____ | ____ | ____ | | 2 | 0 | 1 | ____ | (dd/mm/yyyy)

YES	NO
	

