- Data on the diagnosis of the mRCC patient in CR: date of initial diagnosis of kidney cancer, date of diagnosis of metastatic renal cell carcinoma, nephrectomy, date and type of nephrectomy, World Health Organisation (WHO) pathological classification, TNM classification, tumour size, Furhman nuclear grade, necrosis, vascular embolism, sarcomatoid component;
- Data on the condition of the patient in CR at initiation of Sunitinib: date of initiation, location of metastases, number of metastatic sites; Memorial Sloan-Kettering Cancer Center (MSKCC) prognostic classification;
- CR data: date of achieving CR, method of achieving CR, radiological evaluation of CR using Response Evaluation Criteria in Solid Tumours after the CR.

For Controls

- Data on the inclusion and demographic data: date of signing the consent form, date of consultation, month and year of birth, age, sex, height, weight, inclusion and exclusion criteria;
- Data on the diagnosis of the mRCC patient treated with Sunitinib: date of initial diagnosis of kidney cancer, date of diagnosis of metastatic renal cell carcinoma, date of initiation of Sunitinib, nephrectomy, date and type of nephrectomy, World Health Organisation (WHO) pathological classification, TNM classification, tumour size, Furhman nuclear grade, necrosis, vascular embolism, sarcomatoid component;
- Data on the condition of the mRCC patient before initiation of Sunitinib: blood sample (Yes/No), histology samples (Yes/No) and dates of samples, location of metastases, number of metastatic sites, MSKCC prognostic classification;

Data collected during follow-up visits

In this research, patients will be followed up for three years, according to the usual procedure for this disease (visits every 2 to 3 months in line with the expert opinion set out in the guide to long-term conditions of the French National Health Authority (HAS)).

For Cases

At the visit diagnosing disease progression:

- Date of visit;
- Duration of additional Sunitinib treatment (pseudo-adjuvant), starting at CR;
- Date of progression, type of progression (local or distant);
- Metastatic sites: location and number of metastatic sites;
- Blood sample and collection date;
- Treatment administered after progression (systemic/surgical).

At the annual follow-up visit:

- Date of visit;
- Status of the disease (change);
- Changes in treatment regimen (temporary or permanent discontinuation).

At the end-of-research visit (36 months after the inclusion visit):

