- Visit (Yes/ No);
- Date of visit;
- Best response to treatment received post-progression;
- Duration of administration after progression with first-line Sunitinib;
- Last news: premature discontinuation of study, date of last news, persistent CR since inclusion visit, CR after treatment of post-CR progression, disease progression, number of subsequent lines after progression, post CR;
- Death (Yes/No), date of death.

For Controls

At the 6-month and 12-month follow-up visits of Sunitinib treatment:

- Date of visit;
- Clinical assessment using RECIST criteria (response to treatment, if progression: date of progression, progression at a known metastatic site or at a new site);
- Metastatic sites: location and number of metastatic sites;
- Blood sample and collection date.

If progression:

- Date of visit;
- Date of progression, type of progression (local or distant);
- Metastatic sites: location and number of metastatic sites;
- Blood sample and collection date

At the end-of-research visit (36 months after the inclusion visit):

- Visit (Yes/ No);
- Date of visit;
- Patient still treated with Sunitinib, if yes: response to treatment, if no: progression, new treatment, date of Sunitinib discontinuation;
- Number of subsequent treatment lines;
- Last news: study stopped prematurely, date of last news;
- Death (Yes/No), date of death.

Centralised review of Computerised Tomography Scan (CT Scan) - only for patients in CR

In this research, two of the scans of CR patients (Cases) will be reviewed centrally.

- The scan at initiation of first-line Sunitinib;
- The scan showing CR.

This review will take place between the screening visit and the inclusion visit of the patient. Thus a patient can only be included after the scans have been reviewed to validate the CR.

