4 GENERAL CONSIDERATIONS FOR THE STATISTICAL ANALYSIS OF THE DATA

4.1 Statistical methods

The biostatistics department at AXIAL will perform the statistical analysis, with the exception of the analysis of biological data and biomarkers. Data will be analysed using SAS® software (version 9.4 or later - SAS Institute, North Carolina, USA).

Statistical tests will be carried out bilaterally at a 5% significance level (alpha).

Results will be presented in the form of tables per group (Cases/Controls) presenting:

- For quantitative parameters: number of patients (n), mean and standard deviation, minima and maxima, median and quartiles, and number of missing values.
- For qualitative parameters: number of patients, absolute and relative frequencies for each parameter modality, and number of missing values. Missing data will not be considered when calculating percentages.

Quantitative parameters will be compared between groups using the following methods: Beforehand, the distribution of the parameter will be checked graphically and by using Skewness and Kurtosis and Shapiro-Wilk statistics. If the distribution is considered normal, groups will be compared using a Student's t-test and the difference in means and the 95% Confidence Interval (CI) will be presented. If this is not the case, groups will be compared using a Wilcoxon rank sum test and Hodges-Lehmann estimator, with a presentation of the 95% CI.

For non-ordinal qualitative variables, groups will be compared using the Chi-2 test (or Fisher's exact test if the theoretical numbers <5) and the odds ratio will be presented when specified.

For ordinal qualitative variables, groups will be compared using the Cochran-Mantel-Haenszel test, ridit modified scores ('row mean score differ'). For ordinal qualitative count variables, groups will be compared using the Cochran-Mantel-Haenszel test, 'row mean score differ' table option.

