5 DATA MANAGEMENT CONVENTIONS

5.1 Missing data

Missing data will not be replaced during the data management process and will not be replaced for the statistical analysis, with the exception of the specific cases described in the sections below.

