5.2 Derivative data

The following variables will be calculated:

- Interval between visit X and inclusion (in months):
(Date of follow-up visit X - Date of inclusion visit) / 365.25 x 12.
- Total length of follow-up (in months):
(Maximum date between Date of last visit or Date of last news or Date of death - Date of inclusion visit) / 365.25 x 12.
Note: In case of incomplete dates (date of last news or date of death):
If the day is missing, it will be replaced by the first day of the month.
If the month is missing, it will be replaced by the month of January.
If the date completed is earlier than the last visit carried out, then the date will be replaced by the last visit carried out.
- Age (in years):
Year of inclusion – Year of birth.
- Time of diagnosis of metastatic renal cell carcinoma (in years):
(Date of inclusion visit - Date of diagnosis of metastatic renal cell carcinoma) / 365.25.
Note: In case of incomplete dates (date of diagnosis of metastatic renal cell carcinoma):
If the day is missing, it will be replaced by the first day of the month.
If the month is missing, only the year will be used.
- Time from diagnosis of metastatic renal cell carcinoma to nephrectomy (in months):
(Date of nephrectomy - Date of diagnosis of metastatic renal cell carcinoma) / 365.25 x 12
Note: In case of incomplete dates (date of nephrectomy or date of diagnosis of metastatic renal cell carcinoma):
If the day is missing, it will be replaced by the first day of the month.
- Time between diagnosis of metastatic renal cell carcinoma and initiation of Sunitinib (in months):
(Date of Sunitinib initiation - Date of diagnosis of metastatic renal cell carcinoma) / 365.25 x 12
Note: In case of incomplete dates (Sunitinib initiation date or date of diagnosis of metastatic renal cell carcinoma):
If the day is missing, it will be replaced by the first day of the month.

For Cases:

- Time between diagnosis of metastatic renal cell carcinoma and local treatment (in months):
(Date of local treatment - Date of diagnosis of metastatic renal cell carcinoma) / 365.25 x 12
Note: In case of incomplete dates (date of local treatment or date of diagnosis of metastatic renal cell carcinoma):
If the day is missing, it will be replaced by the first day of the month.
-

- Time between Sunitinib initiation and CR (in years):
(Date of CR - Date of Sunitinib initiation) / 365.25.
*Note: In case of incomplete dates (date of CR or date of Sunitinib initiation):

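### Death is planned only as a Yes/No percentage; if patients leave before 36 months it misstates mortality, and a Kaplan-Meier estimate from dates already collected would not

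*Protocol*

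**What the plan says.** Protocol 8.4, on end-of-study data, states "The number of deaths and the status of patients will be analyzed" and names no method. The SAP supplies it. In 6.4 (Cases) and 6.5 (Controls), death is a Yes/No item described at the end-of-study visit. Under SAP 4.1 such items get counts and percentages, and "Missing data will not be considered when calculating percentages". SAP 5.1 adds "Missing data will not be replaced during the data management process and will not be replaced for the statistical analysis", apart from specific cases, none of which fills in a missing vital status.

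The dates needed for a time-to-event analysis are collected. SAP 2.3 says "In this research, patients will be followed up for three years" and lists for both groups "Death (Yes/No), date of death". For Controls it also lists "Last news: study stopped prematurely, date of last news", and the Case list has a date of last news too. The Case report form (Protocol Appendix 5) tells sites what to do when there is no 36-month visit: "if not, complete the latest information or death form". SAP 5.2 derives total length of follow-up from "Maximum date between Date of last visit or Date of last news or Date of death - Date of inclusion visit", but SAP 6.1 only describes that variable and never joins it to the death indicator.

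The only time-to-event analysis is Kaplan-Meier PFS, run separately in each group. In the SAP 5.2 event tables, death is an event only if no progression came first. SAP 6.4 and 6.5 use the SAP 3.3 population, which requires at least one follow-up visit.

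**The concern.** A Yes/No percentage estimates 36-month mortality only if vital status at 36 months is known for everyone. A patient last heard of alive at month 8 is either coded No, and so counts as alive at 36 months, or is left blank and drops out of the denominator. The first pulls the percentage down. The second pushes it up, because would-be leavers who die first stay in as deaths while those who leave alive are removed. The SAP does not say which coding applies, so even the direction of the error is open.

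PFS does not fill the gap, since a death after progression enters no time-to-event analysis. The population adds a separate problem: a patient who dies before any follow-up visit is not in the death table at all. The first scheduled follow-up visit for Controls is at 6 months.

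What is at stake is a descriptive mortality figure for each group. It is not the comparison of baseline characteristics that forms the primary objective.

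**Working it through.** **Figures in the plan.** The documents state no expected mortality, number of deaths or loss to follow-up, so there is no planned figure to reproduce. The rates below are assumptions.

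**Is early leaving the only source of incomplete follow-up?** Protocol 8.1.2 ends recruitment by December 2018 and follow-up in December 2021. December 2018 plus 36 months is December 2021, so on schedule every patient has 36 months of potential follow-up. The problem therefore comes from early leaving, not staggered entry.

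**Main calculation.** Let S be true 36-month survival with constant hazard h, so 36h = -ln S. A fraction w has a leaving time spread evenly over 0-36 months, unrelated to prognosis.

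- Probability that a would-be leaver dies before leaving: P = 1 - (1 - S)/(36h)
- Reported mortality, leavers coded No: A = (1 - w)(1 - S) + wP
- Reported mortality, leavers blank: B = A / [A + (1 - w)S]

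For S = 0.4: 36h = 0.916 and P = 1 - 0.6/0.916 = 0.345. With w = 0.2, A = 0.8 × 0.6 + 0.2 × 0.345 = 0.549 and B = 0.549/(0.549 + 0.32) = 0.632.

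For S = 0.6: 36h = 0.511 and P = 1 - 0.4/0.511 = 0.217. With w = 0.2, A = 0.8 × 0.4 + 0.2 × 0.217 = 0.363 and B = 0.363/(0.363 + 0.48) = 0.431.

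| True mortality | w | Coded No (A) | Left blank (B) |
|---|---|---|---|
| 60% | 20% | 54.9% | 63.2% |
| 60% | 30% | 52.4% | 65.2% |
| 40% | 20% | 36.3% | 43.1% |
| 40% | 30% | 34.5% | 45.1% |

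The error is 3.7 to 7.6 points low or 3.1 to 5.2 points high. In 80 Controls the low side is 80 × 0.037 = 3 to 80 × 0.076 = 6 deaths. With w = 0, both A and B equal 1 - S and there is no error.

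**Check with a different drop-out model.** Take exponential death and independent exponential leaving, with 36-month probabilities M and D and rates a = -ln(1 - M)/36 and c = -ln(1 - D)/36. Deaths seen = [a/(a + c)] × [1 - (1 - M)(1 - D)]. Lost = [c/(a + c)] × the same bracket. Left blank, the reported figure is deaths seen/(1 - lost).

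| True mortality (D = 20%) | Coded No | Left blank | Kaplan-Meier, 4,000 simulated trials |
|---|---|---|---|
| 10% | 9.0% | 11.1% | 10.1% |
| 20% | 18.0% | 22.0% | 20.1% |
| 50% | 45.4% | 53.2% | 49.8% |
| 70% | 64.1% | 72.8% | 70.1% |

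The simulations used 40 patients for the first two rows and 80 for the last two. Across M = 10-70% and D = 10-30%, the crude figure is 0.5 to 9.1 points low or 0.5 to 5.1 points high. Kaplan-Meier recovers the true value within about 0.2 points in the four scenarios simulated, where leaving is unrelated to prognosis.

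**The case against.** The strongest reply is that survival is neither an objective nor an endpoint. The objectives concern factors associated with CR, treatment after CR, and biomarkers. SAP 2.4 lists patient characteristics, treatment procedure and adverse events. Protocol 8.4 promises a number of deaths, and a count of recorded deaths is correct as a count. This stands, and it limits the point to a reporting improvement.

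A reader might infer that deaths after progression appear nowhere else. The documents do not support that. Protocol section 10 requires a fatal outcome of the malignancy to be recorded as a Grade 5 serious adverse event, and SAP 6.6 tabulates serious events by group. Those tables give counts without time or censoring, however, and use the same followed-up population.

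A reader might also infer that survival of Cases and Controls will be wrongly compared. The plan describes death separately in each group and tests nothing.

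Finally, the plan limits and discloses losses. Protocol 9.3 asks sites to make every effort to document outcome after withdrawal. The SAP reports early termination beside death, and total follow-up by group. This reduces the error and lets a reader see that follow-up is incomplete, but does not correct the percentage. Protocol 9.3 also ends data collection for anyone who withdraws consent to further disclosure, so some losses can remain.

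**Conclusion.** The point holds as a conditional one. If patients leave before 36 months, the planned death percentage is biased, in a direction set by a coding choice the SAP leaves open. Under assumed 40-60% mortality and 20-30% leaving, the error is about 4-8 points low or 3-5 points high. A mixture of the two codings falls in between.

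It would go too far to say that mortality is misstated in both groups. That needs early leaving, for which the documents give no figure. The assumed mortality may also not suit Cases, who are in confirmed CR: at 10% mortality and 20% leaving, the low-side error is about 1 point, or 40 × 0.01 = 0.4 of a patient. The conclusion on factors associated with CR does not depend on any of this. The case for changing the SAP is that a better estimate is available from data already collected, at small cost.

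**What to change.** In SAP 6.4 and 6.5, keep the number of deaths and replace the percentage with a Kaplan-Meier estimate of overall survival in each group.

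- **Population:** all included patients (SAP 3.2). With the clock starting at inclusion, the SAP 3.3 set would omit deaths before a first follow-up visit and credit everyone else with time in which they could not have died.
- **Time and event:** time from the inclusion visit, using the SAP 5.2 follow-up variable; death from any cause is the event; others are censored at last news or last visit. Inclusion is the right origin for Cases because CR may precede it by up to 5 years and patients who died in between could not be enrolled.
- **Output:** survival at 12, 24 and 36 months with 95% CIs, plus the number lost to follow-up.
- **Controls who reach CR:** SAP 2.3 moves them to Cases. Censor them in Controls at the date of CR and let them enter Cases only from that date, so that no time before CR is credited to Cases. At the plan's CR rate of 1.7%, this concerns about 80 × 0.017 = 1.4 patients.
- **Statements to add:** censoring is assumed unrelated to prognosis, and the two curves start at different disease stages and are not compared.

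The cost is SAP wording, a little more programming (including the rule for Controls who change group) and one more table per group. No new data are needed.
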